## Review of PROs

The review of the PRO's should be documented in the patient's source documents.

PRO questionnaires reported on paper, the Haem-A-QOL (and PROMIS in some countries) must be reviewed by the investigator to ensure that all AE's are reported. In addition, the electronically reported Hemo-TEM questionnaires must be reviewed by the investigator to ensure that AE's concerning injection site reactions are recorded in the eCRF at the investigator's discretion. The electronically questionnaire will be available in the eDiary web portal, StudyWorks. The other electronically reported PRO questionnaires do not have to be reviewed by the investigator.

**Table 12      Overview of PRO questionnaires**

| PRO questionnaire as per flow chart                 | Name of questionnaire                                                 | Concept                                                                                                                                                     |
|-----------------------------------------------------|-----------------------------------------------------------------------|-------------------------------------------------------------------------------------------------------------------------------------------------------------|
| SF-36 V2.0 Health Survey                     | 36 Item Short Form Health Survey (SF-36 v2)                           | Generic health state measure, capturing physical and mental health.                                                                                         |
| Patient preference questionnaire             | Haemophilia Patient Preference Questionnaire (H-PPQ)                  | Patient's haemophilia treatment preference                                                                                                                  |
| PROMIS Short Form Upper Extremity            | PROMIS Short Form v. 2.0 Upper Extremity 7a                           | Physical functioning in upper limbs                                                                                                                         |
| PROMIS Numeric Rating Scale - Pain Intensity | PROMIS Numeric Rating Scale v. 1.0 Pain Intensity1a                   | Average pain intensity experienced                                                                                                                          |
| Haemophilia Treatment Experience Measure     | Haemophilia Treatment Experience Measure (Hemo-TEM)                   | Haemophilia specific treatment burden                                                                                                                       |
| Haem-A-QOL)                                  | Haemophilia Quality of Life Questionnaire for Adults                  | Haemophilia specific HRQoL, capturing physical, emotional and social components of HRQoL. For patients <math>\geq 17</math> years only (at visit 1a) |
| PGI-S on physical functioning                | Patient Global Impression of Severity (PGI-S) on physical functioning | Physical functioning level (overall)                                                                                                                        |
| PGI-C on physical functioning                | Patient Global Impression of Change (PGI-C) on physical functioning   | Change in physical functioning level (overall)                                                                                                              |

### 9.2.7      Clinical efficacy laboratory assessments

All protocol-required laboratory assessments, as defined in [Appendix 2](#) and [Appendix 3](#), must be conducted in accordance with the flowcharts in Section 2 and Section 2.1 and the laboratory

manual. The laboratory will provide instructions on sampling, handling of samples, labelling and shipment of samples.

For the efficacy laboratory paraments (concizumab ELISA, Thrombin generation, Free TFPI) a PK/PD profile will be made at visit 2a and visit 9a, for all patients receiving concizumab at visit 2a (patients in arms 2, 3 and 4). See PK/PD sampling flowchart in Section [2.1](#) for further details.

### **Concizumab-ELISA**

Concizumab-ELISA PK profile and trough will be performed as specified in the flowchart see Sections [2](#) and [2.1](#). Samples for assessment of concizumab trough values will be collected pre-dose when patients are assigned to concizumab prophylaxis, i.e. patients in arm 1 will only have baseline samples taken in the main part of the trial. Patients must be instructed to take their daily dose of concizumab after the initial blood sampling have taken place when visiting the site. See Section [9.5](#) for further details.

Validation of the assay followed current bioanalytical guidelines for method validation. The sample taken at visit 4a/9a.2, to determine whether the dose should be adjusted, will be communicated directly to the investigator via a report from the central laboratory (see Section [9.2.2](#)). All other results will be reported to the sites and in a bioanalytical report after the primary analysis cut-off and at the end of the extension part.

### **Thrombin generation**

The Thrombin Generation Assay (TGA) will be performed as specified in the flowcharts in Sections [2](#) and [2.1](#).

In this assay set-up, thrombin generation is initiated by low-dose tissue factor that is combined with phospholipid. The result is obtained by comparison to a constant known thrombin activity in a parallel non- tissue factor-initiated sample. The assay has been validated fit-for-purpose.

Thrombin generation results will be reported at the primary analysis cut-off and at the end of the extension part.

### **Free TFPI**

Free TFPI will be measured as specified in the flowcharts in Sections [2](#) and [2.1](#).

Free TFPI measures TFPI not bound to concizumab. This enzyme-linked immunosorbent assay (ELISA) test will be sampled for at all assessment visits, including 24-hour PK visit. For details please see pharmacokinetics Section [9.5](#).

The assay is commercially available from [REDACTED] ([REDACTED]).

Free TFPI results will be reported at the primary analysis cut-off of the trial and at the end of the extension part.

## 9.3 Adverse events

The definitions of AEs and SAEs can be found in [Appendix 5](#) for the IMP and on demand treatment, and in [Appendix 8](#) for the investigational medical device.

The investigator is responsible for detecting, documenting, recording and following up on events that meet the definition of an AE or SAE.

### 9.3.1 Time period and frequency for collecting AE and SAE information

All AEs will be collected from the first trial-related activity after obtaining informed consent and until end of trial visit, at the time points specified in the flowchart.

[figure not shown]
All SAEs will be recorded and reported to Novo Nordisk or designee within 24 hours, as indicated in [Appendix 5](#) for the IMP and on demand treatment, and in [Appendix 8](#) for the investigational medical device. The investigator must submit any updated SAE data to Novo Nordisk within 24 hours of it being available.

Investigators are not obligated to actively seek for AE or SAE in former trial patients. However, if the investigator learns of any SAE, including a death, at any time after a patient has been discontinued from/completed the trial, and the investigator considers the event to be possibly/probably related to the investigational trial product or trial participation, the investigator must promptly notify Novo Nordisk.

The method of recording, evaluating and assessing causality of AE and SAE and the procedures for completing and transmitting SAE reports are provided in [Appendix 5](#) for the IMP and on demand treatment, and in [Appendix 8](#) for the investigational medical device.

Timelines for reporting of AEs, including AESIs are listed in [Figure 4](#).

Some AEs require additional data collection via a specific event form. This includes medication errors observed during the trial. The relevant specific events are listed in [Table 13](#) and the reporting timelines in [Figure 4](#).

**Figure 4** Decision tree for determining the event type and the respective forms to complete with associated timelines

**Table 13** AEs requiring additional data collection (via specific event form) and AESIsa

| Event type                | AE requiring additional event form | AESI |
|---------------------------|------------------------------------|------|
| Thromboembolic events     |                                    | X    |
| Hypersensitivity reaction | X                                  |      |
| Injection site reaction   | X                                  |      |
| Medication error          | X                                  |      |

aRefer to Section [9.3.6](#) for reporting details

### 9.3.1.1 Adverse event of special interest

The AESIs for this trial are thromboembolic events as listed in [Table 13](#) and must be reported according to [Figure 4](#).

In this trial, the following AEs fulfil the AESI criteria:

- Thromboembolic events including but not limited to,
  - disseminated intravascular coagulation (DIC)
  - thrombotic microangiopathy (TMA)
  - myocardial infarction
  - pulmonary embolism
  - stroke
  - deep vein thrombosis
  - other clinically significant thromboembolic events and peripheral artery occlusion

The AESIs must be reported on an AE form and a safety information form.

The definitions and further information on additional testing on the AESIs and AE requiring additional data collection can be found in [Appendix 5](#).

### **9.3.2 Method of detecting AEs and SAEs**

Care should be taken not to introduce bias when detecting AEs and/or SAEs. Open-ended and non-leading verbal questioning of the patient is the preferred method to inquire about events.

### **9.3.3 Follow-up on AEs and SAEs**

After the initial AE/SAE report, the investigator is required to proactively follow each patient at subsequent visits/contacts. All SAEs, and non-serious AESIs will be followed until resolution, stabilization, or if the event is otherwise explained (e.g. chronic condition) or the patient is lost to follow-up as defined in Section [8.3](#). Further information on follow-up procedures is given in [Appendix 5](#) for the IMP and on demand treatment, and in [Appendix 8](#) for the investigational medical device.

### **9.3.4 Regulatory reporting requirements for SAEs**

Prompt notification by the investigator to Novo Nordisk of a SAE is essential so that legal obligations and ethical responsibilities towards the safety of patients and the safety of a trial product under clinical investigation are met.

Novo Nordisk has a legal responsibility to notify both the local regulatory authority and other regulatory agencies about the safety of a trial product under clinical investigation. Novo Nordisk will comply with country-specific regulatory requirements relating to safety reporting to the regulatory authority, Institutional Review Board (IRB)/ Independent Ethics Committee (IEC), and investigators.

Investigator safety reports must be prepared for SUSARs according to local regulatory requirements and Novo Nordisk policy and forwarded to investigators as necessary.

An investigator who receives an investigator safety report describing a SAE or other specific safety information (e.g. summary or listing of SAEs), from Novo Nordisk will review and then file it along with the IB and will notify the IRB/IEC, if appropriate according to local requirements.

### **9.3.5 Reporting requirement for safety information related to the physical activity tracker**

All safety information and/or other issues judged by the investigator to be related to wearing the activity monitor should be reported by the site directly to the manufacturer ([contact]). If the patient is on a Novo Nordisk product within the haemophilia indication, the safety information must also be reported to Novo Nordisk.

### **9.3.6 Disease-related events and/or disease-related outcomes and other information not qualifying as an AE or SAE**

The following Disease-Related Events (DREs) are common in patients with haemophilia and can be serious/life-threatening:

- Bleeding episodes

## **Bleeding episodes in relation to AE/SAEs**

Because bleeding episodes are associated with the disease under study, they will not be reported according to the standard process for reporting of AEs/SAEs, even though the bleeding episode (event) may meet the definition of an AE/SAE unless they meet the criteria as specified below.

Note: The event must be recorded and reported as an AE/SAE if one of the following applies:

- The event is, in the investigator's opinion, of greater intensity, frequency, or duration than expected for the individual patient.
- The investigator considers that there is a reasonable possibility that the event was related to treatment with the investigational product.
- The event was life-threatening or resulted in death.

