**Table 4 Trial products provided by Novo Nordisk A/S**

|                                                               |                                                           |                                                           |
|---------------------------------------------------------------|-----------------------------------------------------------|-----------------------------------------------------------|
| Trial product name:                                    | Concizumab C 40 mg/ml
(IMP, test product)              | Concizumab C 100 mg/ml
(IMP, test product)             |
| Dosage form:                                           | Solution for injection                                    | Solution for injection                                    |
| Route of administration:                               | Subcutaneous                                              | Subcutaneous                                              |
| Initial (loading) dose - dose at day one:              | 1.0 mg/kg                                                 | 1.0 mg/kg                                                 |
| Dosing instructions daily dose from day 2 and onwards: | Initially 0.20 mg/kg followed by 0.15, 0.20 or 0.25 mg/kg | Initially 0.20 mg/kg followed by 0.15, 0.20 or 0.25 mg/kg |
| Packaging                                              | Prefilled Pen-injector (PDS290 pen-injector)              | Prefilled Pen-injector (PDS290 pen-injector)              |

The investigator must document that directions for use is given to the patient orally and in writing at the first dispensing visit. The investigator, or a person designated by the investigator/institution, will train the patient in the correct use of the investigational product. See Section [7.1.1](#) for further details.

Other haemostatic medication including treatment used for breakthrough bleeds and prophylactic treatment for the screening and follow-up period will not be supplied or reimbursed by Novo Nordisk.

Needles for the pen injector will be delivered as auxiliary. Only needles provided by Novo Nordisk must be used for administration of trial product.

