Only report the bleeding episode as an AE/SAE, (see Section [9.3](#)), if one of the following criteria are fulfilled:

- The event is, in the investigator's opinion, of greater intensity, frequency, or duration than expected for the individual patient.
- The investigator considers that there is a reasonable possibility that the event was related to treatment with the investigational product.
- The event was life-threatening or resulted in death.

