**Table 1 Analysis sets used for analyses and/or presentations of endpoints/assessments**

Endpoint/assessment categories a	Subject Analysis Set	Analysis Data Sets
Bleeding episodes	FAS	On-treatment without ancillary therapy excl. data on initial regimen for subjects exposed to both regimens
PK, PD and safety not relating to events	SAS	On-treatment without data on initial regimen
Safety relating to events b	SAS	On-treatment and On-treatment without data on initial regimen

aWhich endpoints/assessments that belong under each category can be found in section 9 of the protocol version 7.

bThis specifically refers to: number of thromboembolic events, number of hypersensitivity type reactions, number of injection site reactions, number of patients with antibodies to concizumab, and number of adverse events.

For arms 2-4 the target joints registered at baseline will be used for the assessment done at week 56. For arm 1 the target joint evaluation done at visit V9a will be used for assessment at week 56.

Continuous endpoints/assessments will be presented using descriptive statistics which will include min, max, mean, SD, median, and quartiles. For PK endpoints/assessments, the descriptive statistics will also include geometric mean and geometric CV. Event data (including AEs) will be summarised including number of subjects with an event/episode, percentage of subjects with an event/episode, number of events/episodes and rate of events/episodes. Categorical assessments will be summarised by number and percent of subjects in each category. Presentations of results will be by arm and visit (when applicable) and when relevant arm 1 will be split into two parts with on-demand treatment and concizumab treatment.

Baseline for the assessments done at week 56 is defined as the latest non-missing measurement recorded before the time of the first administration of concizumab with the new dosing regimen (arms 2-4 and arm 1 after receiving concizumab) or recorded before randomisation to the on-demand administration (arm 1). If this measurement is missing for arms 2-4 or a subject from arms 2-4 chooses not to restart on concizumab, then the baseline obtained prior to the initial dosing regimen will be used (if available). If the V9a measurement is missing for arm 1 concizumab part,

the latest measurement recorded prior to V9a will be used as a concizumab baseline for arm 1 subjects.

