### **5.6.2 Adverse events**

All exploratory safety endpoints are defined in section [6.2](#).

All adverse events will be coded using the current version of MedDRA. Hypersensitivity reactions, medication errors and injection site reactions are categorised in the CRF as AEs requiring additional data collection. Additional information on these events will be collected using separate forms. Further, a MedDRA search will also be used to define these events. Thromboembolic events are defined and categorised as AESIs.

Adverse events will be evaluated using descriptive statistics based on the analysis data sets as described in section [5.1](#). These descriptive statistics tables will also be presented by treatment arms and 'Total concizumab'.

Furthermore, for the on-treatment analysis data set the outputs on adverse events will also include information on

- System organ class
- Severity (mild/moderate/severe), seriousness (serious/non-serious) and relation to treatment (possibly/probably/unlikely)
- Adverse events leading to drug discontinuation
- Most frequent adverse events (occurring in more or equal to 5% of subjects)
- Deaths
- Medication errors

The outputs may differentiate between the initial part of the trial and the part after the restart of the trial if deemed relevant.

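### Bleeds can become adverse events through a route closed to patients in the on-demand period, so the side-by-side AE columns do not ascertain bleed-derived events by one rule

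*Protocol*

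**What the plan says.** Protocol 9.3.6 treats bleeding episodes as disease-related events and exempts them from the usual AE/SAE process, with exceptions: "The event must be recorded and reported as an AE/SAE if one of the following applies". There are three routes, and any one is enough:

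1. The bleed is, in the investigator's opinion, "of greater intensity, frequency, or duration than expected for the individual patient".
2. "The investigator considers that there is a reasonable possibility that the event was related to treatment with the investigational product".
3. "The event was life-threatening or resulted in death".

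Protocol 9.2.3 repeats the same three routes under the instruction "Only report the bleeding episode as an AE/SAE" when one of them is fulfilled.

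On the analysis side, the SAP's safety analysis set (section 4) contains everyone exposed to concizumab and everyone randomised to on-demand. Appendix 2 defines the number of adverse events for arm 1 on demand, for arm 1 after it starts concizumab, and for arms 2 to 4. Section 5.1 says that event data, AEs included, are summarised by subjects affected, percentage, event count and event rate, and that when relevant "arm 1 will be split into two parts with on-demand treatment and concizumab treatment". Section 5.6.2 adds: "These descriptive statistics tables will also be presented by treatment arms and 'Total concizumab". Neither document provides an AE summary without bleeds, a separate count of AEs that are bleeds, or a note on the unequal rule.

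**The concern.** When an on-demand column stands next to a concizumab column, readers compare them. That comparison is sound only if an event has the same chance of being recorded as an AE in both columns. Bleeding is the condition under treatment, and the planned bleeding rates differ several-fold. A reporting rule that handles bleeds differently by column can therefore shift the AE counts and rates for reasons unrelated to harm. Because the trial is open label, the possible-relation route also depends on a judgement made by an investigator who knows the treatment.

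**Working it through.** There is no stated figure to reproduce. The check sets the passages side by side and then uses simple arithmetic to show what can and cannot be said about size and direction.

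**Who can meet each route**

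- Protocol Table 4 marks only the two concizumab strengths as "IMP, test product", and section 7.1 uses the term investigational product for the pen-delivered drug in that table.
- Protocol 9.3 names the IMP and on-demand treatment as two separate things.
- Protocol 5.2.2 keeps arm 1 on the patient's own bypassing agent until visit 9.
- Protocol Appendix 5 requires causality to be assessed against the trial product.

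Route 2 is therefore closed during on-demand treatment and open during concizumab treatment, including for arm 1 after it switches. Routes 1 and 3 are open in both. The protocol gives no formal definition of investigational product, so this is an inference, but these places leave no other natural reading.

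**Arithmetic**

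Inputs from Protocol 10.1: planned bleeding rate of 18 per year on demand, and *a* = 3 to 5 per year on concizumab. Two quantities are not in the documents and are assumed:

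- *p*: share of bleeds qualifying by route 1 or 3, taken as equal in both columns.
- *q*: share of the remaining bleeds judged possibly related, possible on concizumab only.

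Bleed-derived AEs per patient-year:

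- On demand: 18 × *p*
- Concizumab: *a* × [*p* + *q*(1 − *p*)]

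Route 2 alone (*p* = 0):

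- *q* = 5%, *a* = 3: 3 × 0.05 = 0.15
- *q* = 20%, *a* = 5: 5 × 0.20 = 1.0
- On demand: 0

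These are upper figures for the chosen *q*, because with *p* above 0 some of the same bleeds would already qualify by routes 1 or 3.

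All routes, *p* = 5%:

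- On demand: 18 × 0.05 = 0.90
- Concizumab before route 2: 3 × 0.05 = 0.15 to 5 × 0.05 = 0.25
- Concizumab, *q* = 5%, *a* = 5: 5 × (0.05 + 0.05 × 0.95) = 0.49
- Concizumab, *q* = 20%, *a* = 3: 3 × (0.05 + 0.20 × 0.95) = 0.72
- Concizumab, *q* = 20%, *a* = 5: 5 × (0.05 + 0.20 × 0.95) = 1.20

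Break-even *q*, at which the two columns are equal, is (18*p*/*a* − *p*)/(1 − *p*):

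| *p* | *a* = 3 | *a* = 5 |
|---|---|---|
| 2% | (0.12 − 0.02)/0.98 = 10% | (0.072 − 0.02)/0.98 = 5% |
| 5% | (0.30 − 0.05)/0.95 = 26% | (0.18 − 0.05)/0.95 = 14% |
| 10% | (0.60 − 0.10)/0.90 = 56% | (0.36 − 0.10)/0.90 = 29% |

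Either column can carry more bleed-derived AEs, depending on two shares that the documents do not give.

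**The case against.** The strongest case against has four parts.

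*No AE comparison is planned.* Protocol 4.1.2 sets out to investigate the safety of concizumab, whereas its patient-reported objective is to compare. SAP section 2 tests no hypotheses at week 56, and two of the four arms are not randomised. This stands, and it limits the weight of the point. It does not remove it, because the columns are still shown together with rates.

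*Few bleeds may be attributed to the drug.* Protocol Appendix 5 says lack of efficacy is not in itself an AE. Protocol 3.3 describes a mechanism by which over-activation of coagulation could cause bleeding, and says it has not been seen in trials of concizumab. This also stands: *q* could be well below the illustrated range. The route is nonetheless written into the rule, with a stated mechanism behind it.

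*The planned breakdowns already show it.* For the on-treatment data set, SAP 5.6.2 splits AEs by relation to treatment, seriousness, severity and system organ class. A bleed reported by route 2 would fall among possibly or probably related events. That is a partial answer only. None of these splits identifies which AEs are bleeding episodes, and the overall counts and rates remain mixed.

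*Excluding bleeds hides serious ones.* Removing bleeds from every side-by-side table would drop life-threatening and fatal bleeds, which both columns report by the same criterion. This is right, and it is why bleed-free summaries should be added rather than substituted.

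A reader might also infer that the AE rate difference is biased against concizumab. The documents do not support that. Route 2 alone pushes in that direction, but routes 1 and 3 act on many more bleeds on demand. Nor do the documents show that open-label prophylaxis shifts what an investigator expects under route 1; that is conjecture.

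**Conclusion.** The point holds as a question of comparability. One of the three routes by which a bleed becomes an AE or SAE is closed during on-demand treatment, so the bleed-derived part of the AE counts and rates is not ascertained by the same rule in the two columns. Taken alone, the route can only add events on concizumab. Its size is unknown because the documents give no attribution rate; 0.15 to 1.0 per patient-year is an illustration at an assumed 5% to 20%. The net direction between columns is also unknown: with 5% of bleeds qualifying by the shared routes, concizumab overtakes on-demand only if attribution exceeds about 14% to 26%.

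The consequence is limited. The week-56 tables are descriptive, and the bleed endpoints are unaffected because Protocol 9.2.3 records every bleed whether or not it is an AE. The conclusion rests on reading investigational product as concizumab. The SAP for the primary analysis cut-off and the mock tables were not available, so their layout could not be checked.

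**What to change.** In SAP 5.6.2:

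- Keep the all-AE tables as planned.
- Wherever arm 1 on demand appears beside concizumab, add the same AE and SAE summaries excluding AEs that are bleeding episodes. Injection site reactions stay in, including the haematoma and bleeding that Protocol 9.4.9 counts among them.
- Add a listing by arm, with arm 1 split by treatment period, of AEs that are bleeding episodes, showing recorded relatedness, severity and seriousness. Life-threatening and fatal bleeds then remain visible.
- State in a footnote that the possible-relation route does not apply during on-demand treatment.

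The listing should use recorded relatedness and seriousness, not the criterion that triggered reporting, because neither document says that criterion is recorded. Define in advance how an AE is matched to a bleed record.

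Apply the same change to the primary-cut-off tables if they share this layout. The cost is one extra set of tables, one listing and the matching rule. The downside is two versions of the AE summary to present.
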